#### 7.4.1.1 Secondary Analyses

The incidence of subjects with prostate cancer progression (pathological or therapeutic) will be summarized with frequencies and percentages at one year, two years, and study completion. Treatment group differences will be assessed using a logistic regression with the same covariates and random effect used in the primary analysis and include two-sided 95% confidence interval estimates of the odds ratio.

In addition to an overall analysis, the primary and secondary analyses will be repeated for pathological progression and therapeutic progression, individually.

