## 4 SAMPLE SIZE

This study is designed to evaluate time to prostate cancer progression (pathological or therapeutic progression) as the primary endpoint. The overall two-sided type I error for this study is set at 0.05 level. The characteristics of time to prostate cancer progression (pathological or therapeutic progression) are used to determine the total sample size and overall duration.

A sample size of 222 subjects randomized in a 1 to 1 manner accrued over one year, a study duration of 3 years, loss-to follow-up of 16%, an assumed underlying hazard ratio of 0.52 and a three year median time-to-progression for the Control group (0.2310 rate) will result in 72 events (Fleshner et al., 2012). This sample size is sufficient to power this study at 80% with a two-sided type I error rate of 5%.

The assumed hazard ratio of 0.52 is consistent with Fleshner et al. (2012). Specifically, the Fleshner study is powered to detect a 39% failure rate reduction in the treated group with respect to a three year 45% failure rate in the control group. We used a more conservative 30% failure rate reduction for the treated group and a 50% three year failure rate for the control group. This resulted in parameter estimates of 0.2310 for the Control group and 0.1189 for the Treatment group, and thus, resulted in the hazard rate of 0.52.

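### The logistic comparison of progression incidence cannot use censoring times, and the SAP does not say how men lost before a time point are counted; if loss differs by arm, that unstated choice sets the direction of the bias in the odds ratio

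*SAP*

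**What the plan says.** Section 7.4.1.1 summarizes the incidence of progression "at one year, two years, and study completion" and adds a between-arm test: "Treatment group differences will be assessed using a logistic regression with the same covariates and random effect used in the primary analysis", reported as an odds ratio with a 95% confidence interval. The same section repeats this for pathological and therapeutic progression separately, and section 7.4 runs all efficacy analyses on both the FAS and the PPS.

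The censoring rules are in section 7.4.1. Men without progression are censored at the last assessment, and men who switch therapy are censored at the first switch. They are written for the Kaplan-Meier estimates and extended to the Cox model. Section 7.4.1.2 explicitly brings them into the subgroup analyses. Section 7.4.1.1 carries over only the covariates and the site random effect.

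Two general rules might apply. Section 7.1 bases percentages on subjects without missing data unless specified otherwise, and section 7.10.1 rules out imputation and relies on available data. Section 4 plans for "loss-to follow-up of 16" per cent overall, with no split by arm. Section 3.2 describes an open-label trial in which men are followed past two years until the last man completes his 24-month visit.

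**The concern.** A time-to-event outcome is turned into yes/no at each time point. For a man lost at month 15 without progression, two-year status is unknown. Counting him as not progressed lowers his arm's incidence. Dropping him raises it, because men who progressed before they could be lost stay in both numerator and denominator. If both arms lose men at the same rate, the two distortions nearly cancel in the odds ratio. If not, they do not cancel.

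Unequal loss is plausible here, because the trial is open label and one arm takes a daily drug while the other takes none. At stake is an odds ratio with a confidence interval that readers will set beside the hazard ratio, and that could differ from it through loss and coding alone.

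The study-completion figure raises a separate matter of interpretation. With one year of accrual and a common study end, follow-up runs from about two to three years, so the proportion refers to no fixed time.

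**Working it through.** **Inputs from SAP section 4.** "A sample size of 222 subjects randomized in a 1 to 1 manner accrued over one year, a study duration of 3 years"; "an assumed underlying hazard ratio of 0.52 and a three year median time-to-progression for the Control group (0.2310 rate) will result in 72 events"; "This resulted in parameter estimates of 0.2310 for the Control group and 0.1189 for the Treatment group"; 16% loss. With 1:1 allocation there are 111 men per arm.

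**1. Reproduce the plan's 72 events.** The hazards follow from the stated failure rates: ln(2)/3 = 0.2310 and −ln(1 − 0.30)/3 = 0.1189 per year. Read 16% as loss over three years in both arms, so the loss hazard is δ = −ln(0.84)/3 = 0.0581. With exponential times, the probability of observed progression by time t is

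P(t) = λ/(λ+δ) × [1 − exp(−(λ+δ)t)].

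Averaged over follow-up uniform on 2 to 3 years, this is 0.4098 (control) and 0.2396 (enzalutamide). Then 111 × (0.4098 + 0.2396) = 72.1 events. With no loss the figure is 77.1. Spreading the 16% over three years therefore matches the SAP's own calculation.

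**2. No treatment effect, unequal loss (an assumption).** Set λ = 0.2310 in both arms. Let three-year loss be 22% on enzalutamide and 10% on surveillance, which averages 16%. The loss hazards are −ln(0.78)/3 = 0.0828 and −ln(0.90)/3 = 0.0351.

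- Coding A, lost men counted as not progressed: incidence = P(t).
- Coding B, lost men dropped: incidence = P(t) / [P(t) + exp(−(λ+δ)t)].

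At two years under A, enzalutamide gives 0.2310/0.3138 × (1 − exp(−0.6277)) = 0.343 and surveillance gives 0.2310/0.2661 × (1 − exp(−0.5322)) = 0.358. The odds ratio is (0.343/0.657)/(0.358/0.642) = 0.94.

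| Time point | True incidence, both arms | A: enz. vs AS | A: OR | B: enz. vs AS | B: OR |
|---|---|---|---|---|---|
| 1 year | 20.6% | 19.8% vs 20.3% | 0.97 | 21.3% vs 20.9% | 1.03 |
| 2 years | 37.0% | 34.3% vs 35.8% | 0.94 | 39.1% vs 37.9% | 1.05 |
| Study completion (2–3 years) | 43.7% | 39.9% vs 42.0% | 0.91 | 46.5% vs 44.9% | 1.07 |

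The true odds ratio is 1 throughout.

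**3. Range over the assumed split, still with no effect.**

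- 16% / 16%: 1.00 at every time point under both codings.
- 27% enzalutamide / 5% surveillance: A gives 0.95, 0.89, 0.85; B gives 1.05, 1.10, 1.13.
- 10% enzalutamide / 22% surveillance: at two years A gives 1.07 and B gives 0.95, so the directions swap.

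**4. Under the planned effect.** The true two-year incidences are 21.2% and 37.0%, an odds ratio of 0.457. Equal 16% loss gives 0.463 (A) or 0.456 (B). Loss of 24% enzalutamide / 8% surveillance gives 0.427 (A) or 0.489 (B).

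**5. Size against sampling error.** For the 22% / 10% split at two years under A, the standard error of the log odds ratio is √[1/(111 × 0.343 × 0.657) + 1/(111 × 0.358 × 0.642)] = 0.281. The shift is ln(0.936) = −0.066, or 0.24 standard errors, which takes a nominal 5% two-sided test to about 5.6%. In simulations of an unadjusted test with a 24% / 8% split (20,000 trials per setting), the rate at study completion was about 7.0% under A and 6.0% under B.

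**The case against.** The strongest reply is that little hangs on this analysis. It is a secondary look at the primary endpoint in a study the SAP calls exploratory. The Kaplan-Meier and Cox results, which handle censoring, stand beside it. The split by arm is assumed, since the SAP gives one overall figure. At the moderate split the shift is a quarter of a standard error at two years, and smaller at one year. Kaplan-Meier also assumes independent censoring, so the repair does not remove informative dropout. All of this stands, and it limits the weight of the point.

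It could also be said that sections 7.1 and 7.10.1 already settle the coding in favour of dropping. They lean that way but do not decide it: a man with no progression recorded before he left could be read as a missing value or as a recorded no. Even if dropping is meant, the odds ratio is still biased under unequal loss, only in the other direction.

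A reader might infer that the plan favours enzalutamide. The documents do not support that, because direction depends on which arm loses more men and on the unstated coding. A reader might also infer that the spread of two to three years of follow-up biases the study-completion odds ratio. It does not do so by itself, since randomization balances accrual time between arms. Applying three years to everyone would also overstate the study-completion shift (0.89 instead of 0.91 under coding A).

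**Conclusion.** The point holds within limits. Section 7.4.1.1 uses a method that cannot take account of censoring and gives no rule for men lost or switched before a time point. At the 22% / 10% split with no true effect, the odds ratio is off by about 3% at one year, 5% to 6% at two years and 7% to 9% at study completion. It falls below 1 under one coding and above 1 under the other. With equal loss the bias is negligible. The primary analysis is not affected.

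The sizes rest on exponential times, loss independent of progression and spread over three years, and an assumed split. They treat progression as detected continuously. Because pathological progression is found mainly at the 12- and 24-month biopsies, the exact sizes would differ, but the mechanism would not. The study-completion proportion is hard to interpret because it refers to no fixed time; that is not a bias.

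**What to change.** In section 7.4.1.1, make the one- and two-year comparison the Kaplan-Meier probability of progression in each arm, with the between-arm difference and 95% CI, under the censoring rules of section 7.4.1. Where covariate adjustment is wanted, use pseudo-value regression with the same covariates; the site random effect then needs a counterpart, such as site-clustered standard errors.

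Set the time points late enough to include the 12- and 24-month biopsies. The upper ends of the section 7.10.3 windows, days 406 and 754, would do so. Exactly two years is day 730.5 under the SAP's 365.25-day year, which would cut off biopsies taken within the allowed week after day 730.

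Keep any study-completion proportion as description, without a test. If the odds ratio is kept as a supplement, state how men lost or switched before each time point are coded, and report the other coding as a sensitivity analysis.

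The cost is a change of wording and some programming on Kaplan-Meier output that is already planned. Odds ratios give way to risk differences. Independent censoring is still assumed, so informative dropout would need its own sensitivity analysis.

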#### 7.4.1.2 Subgroup Analysis

Subgroup analyses of time to progression will be performed to evaluate the treatment effect based on the following subgroups: age (<65, 65 to <75, and  $\geq 75$ ), race, and BMI at screening

(<25; 25-30; and >30). Kaplan-Meier methods, Cox regression models and censoring rules described in section 7.4.1 will be used for each analysis. Summary tables will be presented.

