### 7.4.1 Analysis of Primary Endpoint(s)

The primary efficacy endpoint is time to prostate cancer progression (pathological or therapeutic), and the hypothesis for analysis is:

$H_0$ : The time to progression for Enzalutamide and Active Surveillance (AS) are the

same  $H_1$ : The time to progression for Enzalutamide and AS are not the same

Median and 95% confidence intervals for time to prostate cancer progression (pathological or therapeutic) will be calculated with the Kaplan-Meier (KM) method for each treatment group. Subjects with no cancer progression at the time of trial completion, discontinuation or death will be censored at the last assessment date. Additionally, subjects switching therapy during the study will be censored at the time of the initial therapy switch, but subjects discontinuing therapy will not be censored until the time of study discontinuation. If less than 50% of subjects progress by study cut-off time, the 25th percentile and its two-sided 95% confidence interval will be reported. KM plots will be generated.

Treatment group differences between enzalutamide versus AS will be based on a Cox regression model. The resulting Hazard ratio (enzalutamide/AS) and 95% confidence interval will be included in the summary. Censoring assumptions will follow the same rules as applied for the KM estimates. Fixed effects for the model will include the treatment groups, randomization stratification factors [prostate cancer risk (low/intermediate), type of biopsy performed (mpMRI targeted/non mpMRI targeted)], age, race, and time since prostate cancer diagnosis. Additionally, a random effect of site will be included in the model.

The association between the survival time, log of time to disease progression, and survival probability, log negative log, will be investigated graphically by Cox proportional-hazards models. If the proportional hazards assumption is violated, appropriate remedial methods will be investigated and applied.

Data listings will be provided.

In addition to an overall analysis, the primary and secondary analyses will be repeated for pathological progression and therapeutic progression, individually.

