## 8 SAP DEPARTURES FROM THE PROTOCOL

- [REDACTED] *CCI*  
[REDACTED]
- Primary and secondary analysis will be done separately for therapeutic and pathological progression, in addition to overall.
- FAS and SAF would be different in the case of subjects randomized to enzalutamide treatment group end up discontinuing before taking a single dose of the study drug
- It is unlikely but possible to have dose increases. Such a possibility has been accounted for in the relevant table and listing.
- “Age” will be an additional fixed effect used in the statistical models.
- “Site” will be an additional random effect used in the statistical models.
- [REDACTED] *CCI*
- ENACT study is conducted in patients with localized disease who are candidate for Active Surveillance, the use of questionnaire such as BFI, SF-12, MAX-PC and EPIC have not been validated in this patient population, as a result analysis of PROs will be limited to descriptive statistics. The details of descriptive analyses can be found in respective PRO sections.
- All analyses will be performed separately by stratification factors [prostate cancer risk (low/intermediate) and type of biopsy performed (mpMRI targeted/non mpMRI targeted)].

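### Subgroup and by-stratum hazard ratios come from refitting the full primary Cox model in small subsets, with no treatment-by-factor interaction

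*SAP*

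**What the plan says.** Section 7.4.1 defines the primary Cox model. Its fixed effects are treatment, risk group, biopsy type, age, race and time since diagnosis, followed by: "Additionally, a random effect of site will be included in the model".

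Section 7.4.1.2 carries this into the subgroups: "Kaplan-Meier methods, Cox regression models and censoring rules described in section 7.4.1 will be used for each analysis". Section 7.8 confirms that the subgroups are taken separately and gives three levels each for age, race and BMI.

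For the randomization strata the SAP says two things. Section 7.4.1.3 has the time-to-progression analyses include risk group and biopsy type so that their effects can be evaluated. Section 8 goes further: "All analyses will be performed separately by stratification factors", naming the same two factors.

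The SAP does not reduce the model for small subsets, drop a factor that is constant within a subset, or label these results exploratory. Its only interaction term is time-by-treatment in the repeated-measures model of section 7.4.2.3.

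**The concern.** Section 1.1 says the study will examine the effect of enzalutamide in different subsets of subjects, and section 7.4.1.2 gives evaluation of the treatment effect as the purpose of the subgroups. The stated method serves that aim poorly in three ways.

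- The model was specified for 72 events. Refitted in a third or a fifth of them, it has few events per parameter, and the site variance is barely estimable.
- Some covariates become constant: race within a single-category race level, and risk group or biopsy type within its own stratum. They then drop out, so the model as written is not the model fitted.
- Hazard ratios from separate fits sit side by side with no estimate of the difference between them. Whether the effect varies is left to the eye.

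If a fit fails, the SAP names no fallback, so in this open-label trial the replacement model would be chosen after the data are seen.

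**Working it through.** **Inputs (SAP).** Section 4: "The overall two-sided type I error for this study is set at 0.05 level"; 80% power; "an assumed underlying hazard ratio of 0.52"; "parameter estimates of 0.2310 for the Control group and 0.1189 for the Treatment group"; "A sample size of 222 subjects randomized in a 1 to 1 manner accrued over one year"; 3-year duration; 16% loss; 72 events. Section 3.2: about 50 centers. Section 3.3: low risk at most 80% of enrollment.

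**1. Reproduce the planned events.**
- Unrounded hazard ratio: 0.1189/0.2310 = 0.5147.
- Required events: 4 × (1.960 + 0.842)² / (ln 0.5147)² = 31.4/0.441 = 71.2, rounded up to 72.
- Expected events, with exponential times, uniform one-year accrual and 16% exponential loss over 3 years: event probability is about 0.410 on control and 0.240 on treatment, so 111 × (0.410 + 0.240) ≈ 72.1.

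The figure of 72 is sound and is used below.

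**2. Count parameters.** Treatment 1, risk 1, biopsy type 1, age 1, race 2, time since diagnosis 1: 7 fixed effects, assuming linear age and time and three race categories. The site effect adds one variance.

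**3. Events by subset.** Overall there are 72/7 = 10.3 events per fixed effect and 72/50 = 1.4 per site. The smallest of three levels cannot exceed 72/3 = 24 events, or about 0.5 per site. At the low-risk cap, intermediate risk has 0.20 × 222 ≈ 44 men. The SAP gives no subgroup counts, so the 10% and 5% rows are assumed shares, and events are taken as proportional to share. The interval is 0.52 × exp(±1.96 × 2/√d) for d events, without covariates.

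| Share | Events d | d/7 | 95% CI around 0.52 |
|---|---|---|---|
| 80% (low risk at cap) | 57.6 | 8.2 | 0.31 to 0.87 |
| One third | 24 | 3.4 | 0.23 to 1.16 |
| 20% (intermediate-risk minimum) | 14.4 | 2.1 | 0.19 to 1.46 |
| 10% | 7.2 | 1.0 | 0.12 to 2.24 |
| 5% | 3.6 | 0.5 | 0.07 to 4.10 |

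Where a factor is constant the count eases a little. Within a risk stratum 6 fixed effects remain, so 14.4/6 = 2.4.

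**4. Does the full model fit?** Two simulations, both without the site effect and with assumed covariate shares, gave these rates of failed fits (first simulation: failed or separated, 500 runs per size):

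| Events (about) | Separate 7-covariate fit, first | Separate 7-covariate fit, second | Pooled interaction model, second |
|---|---|---|---|
| 24 to 25 | 8% | 5% | 1% |
| 14 | 12% | 13% | 1% |
| 7 | 23% | 36% | 7% |
| 4 | 83% | 78% | 36% |

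At 72 events the first simulation failed in 0.2% of runs. In the second, root mean squared error of the log hazard ratio fell from 0.76 to 0.63 at 14 events, and from 1.42 to 0.90 at 7, on moving from separate fits to the pooled model.

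**5. Scatter under a constant effect.** If 0.52 holds everywhere, the chance that a subset shows a hazard ratio above 1 is Φ(−0.654√d/2): 5.5% at 24 events, 11% at 14.4 and 19% at 7.2.

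**6. What an interaction test can detect.** For a two-level factor the standard error of the log ratio of hazard ratios is √(4/d₁ + 4/d₂).
- 50:50 split of events: 0.471. Power for 0.52 against 1.0 is Φ(0.654/0.471 − 1.96) = 28%. The ratio detectable with 80% power is exp(2.80 × 0.471) ≈ 3.8.
- 80:20 split: 0.589. Power is 20% and the detectable ratio is 5.2.

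**The case against.** The other side has real points.

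- A reader might infer that every subset holds only a handful of events. The SAP does not support that. A three-level factor averages 24 events per level, low risk could hold about 58, and single digits need a level with roughly 12% of events or fewer. Small age or race levels are plausible but assumed.
- The wide intervals are not evidence against refitting. An interaction model draws on essentially the same events in that level, so a subset with 14 events stays imprecise either way.
- A reader might take the random effect for some 50 extra parameters. It is one variance; the trouble is the sparse information per site.
- The constant-covariate point is limited. BMI is not in the section 7.4.1 model, and age still varies within an age band if entered as continuous. A constant term drops out without biasing the treatment effect.
- Section 7.4.1.2 covers only age, race and BMI. The by-stratum analyses rest on section 8, which does not itself name a model.
- An interaction test with 20% to 28% power will usually be non-significant even when effects differ, and that could be misread as consistency.
- Section 3.2 calls the study exploratory, and section 7.4.1 supplies confidence intervals, so imprecision will be visible.

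All of this narrows the point, but it does not answer it. The full model is still carried into subsets for which it was not sized, the difference between subsets is never estimated, and the pooled model failed less often and had smaller error at the sizes compared.

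**Conclusion.** The concern holds in limited form. Sections 7.4.1.2 and 7.8 prescribe separate refits of the full primary Cox model within age, race and BMI levels. Section 8 extends separate analysis to risk group and biopsy type, in tension with section 7.4.1.3. At no more than 24 events in the smallest of three levels, and possibly 14 in intermediate risk, that model is over-parameterized and will sometimes fail. It does not answer whether the effect differs.

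The size rests on 72 events, the 7-parameter count, events proportional to share, and simulations with assumed covariate shares and no site effect. It would be wrong to say that these fits will generally fail. In the simulations failure was the usual result only near 4 events, which needs an assumed 5% subset.

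The primary test and the 72-event calculation are untouched. This is a change that should be made to secondary analyses, not a threat to the main conclusion.

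**What to change.** In sections 7.4.1.2 and 7.8, replace the separate refits with the overall section 7.4.1 Cox model plus one treatment-by-factor interaction at a time. Include the factor's main effect where the model lacks it, as for BMI and for age in bands. Report each level's hazard ratio with its 95% CI, and the interaction estimate and p-value. Keep Kaplan-Meier curves by level as description, and label the results exploratory.

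Treat risk group and biopsy type the same way, and reconcile section 7.4.1.3 with section 8 so that the SAP states one method for the strata. A minimum event count, set before database lock, would be a sensible addition, because the pooled model also failed often near 4 events. Below that count, show only event numbers and curves.

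The cost is SAP wording and modest, probably simpler, programming. The SAP should state three downsides: covariate effects are assumed common across subgroups; the interaction test has low power, so a non-significant result does not show consistency; and small subgroups remain imprecise.

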#### **7.4.1.3 Stratification Factors**

Analyses of time to progression will include randomization stratification factors to evaluate their effects. These factors are prostate cancer risk (low and intermediate) and type of biopsy performed (mpMRI targeted and non-mpMRI targeted).

